7.2 Analysis and Presentation of the Secondary Endpoints

The secondary endpoints are

- (A-a)DO₂ during the trial
- 6 Minute Walk Distance (6MWD) during the trial
- St Georges Respiratory Questionnaire (SGRQ) total score during the trial
- Frequency of Whole Lung Lavage (WLL) during the trial
- Diffusion Capacity of the Lung for Carbon Monoxide (DLCO) (% predicted), FEV1 (% predicted), and FVC (% predicted) during the trial
- PaO₂ and disease severity score (DSS) during the trial
- Need for oxygen supplement therapy during the trial
- Overall clinical assessment (status of aPAP and requirement for treatment since last visit)
- Number of subjects not requiring treatment for aPAP and time off treatment after discontinuation of inhaled molgramostim

7.2.1 Blood Gas Analysis

The following variables will be assessed from an arterial blood gas sample collected at the timepoints shown in Table 1.

- PaO₂ (mmHg) – arterial partial pressure of oxygen
- PaCO₂ (mmHg) – arterial partial pressure of carbon dioxide
- F_iO₂ – fraction of inspired oxygen

P_{atm} (ambient atmospheric pressure) must be collected using a bedside barometer. The P_{H₂O} (saturated vapor pressure of water at body temperature) will be set to 47 mmHg / 6.266 kPa.

The Aa Gradient (A-a)DO₂ will be calculated centrally using the following formula:

$$Aa\ Gradient = \left(F_i O_2 (P_{atm} - P_{H_2O}) - \frac{P_a CO_2}{0.8} \right) - P_a O_2$$

The Aa Gradient will be summarized by visit. A corresponding mean and with confidence interval (CI) plot over time will be provided. Subjects on supplementary oxygen during blood gas sample are excluded from the relevant visits in the summary.

A corresponding listing by subject and visit will be provided including all subjects regardless of use of supplemental oxygen.

Any Aa Gradients reported in kPa will be converted to a result in mmHg, this will be done using a factor $k=7.5$ ($kPa \times 7.5 = mmHg$).

7.2.2 6-minute Walk Test (6MWT)

Exercise capacity will be assessed using the 6MWT to measure the 6-minute walk distance (6MWD) at the timepoints shown in Table 1.

The 6MWT should be performed twice at each visit in accordance with the European Respiratory Society (ERS)/American Thoracic Society (ATS) guidance.

Data from both tests should be entered in the eCRF. Parameters to be recorded comprise pre and post walk dyspnea score using the Borg (CR-10) Dyspnea Score (including the difference post minus pre dyspnoea score), SpO₂ (%) at start, worst SpO₂ (%) during the walk, distance walked (m), duration of the walk (minutes and seconds), oxygen flow rate if applicable, reason for stopping early (if applicable). For each subject and each visit the results from the test with the longest distance walked will be used in the reporting of the trial.

Distance in meter, Borg score endpoints, and SpO₂ and the desaturation (first SpO₂-worst SpO₂) will be summarized by treatment and visit. Furthermore, number of subjects (N, %) who completed the test will be presented by treatment and visit.

A corresponding mean and CI plot over time as well as a corresponding listing by subject and visit will be provided for each of the endpoints.

The listing will include pre and post walk dyspnoea Borg (CR-10) score, start and worst SpO₂ (%), distance walked, duration, oxygen flow rate (L/min), use of oxygen supplementation during the test (yes/no), and stopping early (yes/no) including the reason for stopping early. Both 6MWT at each visit will be included in the listing.

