4. INTRODUCTION

4.1. Background

Pulmonary alveolar proteinosis (PAP) is a rare autoimmune disease with an estimated prevalence of 0.7 per 100,000 individuals [Trapnell 2014]. It is characterised by high levels of autoantibodies against Granulocyte Macrophage Colony Stimulating Factor (GM-CSF) in alveoli and blood. The autoantibodies neutralise the normal biologic action of GM-CSF in the lungs [Khan 2012]. Pulmonary Alveolar Proteinosis is also characterised by the accumulation of Periodic Acid-Schiff (PAS)-positive lipoproteinaceous material, primarily phospholipid surfactant, and surfactant apoproteins in the distal air spaces. Consequently, gas transfer is decreased leading to impairment of gas exchange, respiratory failure, and to increased risk of respiratory infections [Trapnell 2014, Rosen 1958, Trapnell 2003, Inoue 2008]. More than 90% of the reported cases of PAP are classified as the autoimmune disorder type associated with GM-CSF autoantibodies (aPAP). Less common are the secondary and congenital types [Trapnell 2003, Inoue 2008].

No evidence-based curative treatment exists for patients with PAP. There is, therefore, a need for new and modern treatment approaches for PAP patients. Sequential whole lung lavage (WLL) under general anaesthesia has become the standard of care. Whole Lung Lavage decreases the symptoms and improves the oxygenation in PAP patients. It is not possible to predict how many WLL treatments a particular patient will need; a single WLL is sufficient for some patients while others require lavage every six to 12 months for many years. The observation that mice deficient in the gene for GM-CSF develop alveolar accumulations of surfactant substances similar to that seen in PAP led to the suggestion of a potential role for recombinant human GM-CSF (rhGM-CSF) in the treatment of PAP [Dranoff 1994].

Investigational Medicinal Product (IMP)

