7.3. Subject Withdrawal Criteria

7.3.1. Discontinuation of Trial Treatment

Subjects may be discontinued from treatment and assessments at any time, if deemed necessary by the investigator. Potential reasons for discontinuation of treatment are:

- Remission of aPAP
- Lack of efficacy/worsening of disease (e.g. loss of response that requires a different treatment modality).
- Unacceptable AE (including serious hypersensitivity reaction).
- Pregnancy.

Those who discontinue treatment will not automatically be withdrawn from the trial but will be encouraged to continue to follow the same visit schedule. If medically indicated and no safety-related exclusion criteria have emerged, treatment may be restarted at a later visit.

The reason and date the subject is discontinued will be documented in the electronic case report form (eCRF).

Subjects who fulfil the criteria for rescue treatment will be scheduled for a WLL as described in Section 10.2. Subjects receiving a WLL should continue treatment and attend the remaining visits, unless discontinuation is medically required, according to investigator's discretion.

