10.7.7. Whole Lung Lavage

At each visit, information on whether WLL is required will be recorded. The criterion for performing WLL is clinical worsening of aPAP based on symptoms, reduced exercise capacity and/or findings of hypoxemia or desaturation according to the investigator's judgement. The reason(s) for WLL requirement will be documented.

Information about any WLL actually performed must be reported in the eCRF. The following information will be entered. Date of the WLL and type of WLL (unilateral, bilateral) will be recorded. Information about other assessments performed (e.g. blood gas measurements, lung function tests and exercise tests) before and after a WLL is performed should also be recorded.

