3.1.2 Secondary Objectives

The secondary objectives are

- To investigate effects of long-term use of inhaled molgramostim on oxygenation.
- To investigate effects of long-term use of inhaled molgramostim on exercise capacity.
- To investigate effects of long-term use of inhaled molgramostim on respiratory quality of life.
- To investigate requirement for WLL during long term use of inhaled molgramostim.
- To investigate effects of long-term use of inhaled molgramostim on lung function.
- To investigate maintenance of effect after discontinuation of inhaled molgramostim.

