3.2 Trial Design

The trial is an open-label, non-controlled, multi centre clinical trial of inhaled molgramostim in autoimmune pulmonary alveolar proteinosis (aPAP) patients.

Subjects with aPAP who have completed the IMPALA (MOL-PAP-002) trial will be eligible for this trial.

At the baseline visit, eligible subjects may continue or re-start treatment with inhaled molgramostim (300 µg) administered intermittently in cycles of seven days molgramostim, administered once daily, and seven days off treatment.

Trial visits will be conducted at 6-monthly intervals until the end of trial. Participating subjects will be encouraged to contact the clinic between visits if they experience adverse events (AEs) or worsening of aPAP, or if they have any other concerns.

During the trial, Whole Lung Lavage (WLL) will be applied as rescue therapy. The criterion for performing WLL is clinical worsening of aPAP based on symptoms, reduced exercise capacity and/or findings of hypoxemia or desaturation according to the investigator's judgement. The reason(s) for conducting WLL will be documented. Subjects undergoing WLL will continue treatment with molgramostim, unless discontinuation is medically required, according to investigator's discretion.

Subjects may discontinue molgramostim due to remission of aPAP, lack of response that requires a different treatment modality, or AEs. Subjects becoming pregnant will be required to discontinue treatment with molgramostim. Subjects who discontinue molgramostim will be encouraged to continue in the trial and attend visits according to the same schedule until end of the trial. Molgramostim treatment may be re-started if medically required. Subjects not requiring treatment at the Baseline visit may start molgramostim treatment during the trial if medically required.

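### The by-visit efficacy summaries include values taken after rescue lavage, neither labelled nor split, while the objectives present them as effects of molgramostim

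*SAP*

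**What the plan says.** On lavage, SAP 3.2 states: "During the trial, Whole Lung Lavage (WLL) will be applied as rescue therapy". It is given for worsening, as the investigator judges. Lavaged subjects normally stay on drug: "Subjects undergoing WLL will continue treatment with molgramostim, unless discontinuation is medically required, according to investigator's discretion". Protocol 7.3.1 adds that "Subjects receiving a WLL should continue treatment and attend the remaining visits", with the same exception. Protocol 4.1 gives the expected effect: "Whole Lung Lavage decreases the symptoms and improves the oxygenation in PAP patients".

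On the objective, SAP 3.1.2 has "To investigate effects of long-term use of inhaled molgramostim on oxygenation", with parallel objectives for exercise capacity, quality of life and lung function.

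On the summaries, SAP 7.2.1 has "The Aa Gradient will be summarized by visit". SAP 7.2.2 (6MWD), 7.2.3 (SGRQ), 7.2.5 (DLCO, FEV₁, FVC) and 7.2.6 (DSS) also summarise by visit or over time. SAP 4 assigns efficacy to the full analysis set and uses observed data without imputation. The one condition that removes a value is oxygen at the blood gas sample: "Subjects on supplementary oxygen during blood gas sample are excluded from the relevant visits in the summary". SAP 7.2.6 has the same rule for DSS.

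Lavage has its own outputs: subjects and events by visit and overall with rates (SAP 7.2.4), a treatment-requirement table by visit that includes lavage as a category (SAP 7.2.8, Table 14.2.8.2), and Listing 16.2.6.4. Protocol 10.7.7 also asks that other assessments "before and after a WLL is performed should also be recorded".

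**The concern.** Rescue is triggered by worsening and, on the protocol's own account, reverses part of it. Visits are six months apart. A subject can deteriorate, be lavaged between two visits and contribute only the post-lavage value to the next summary. That value reflects drug and procedure together, and in an uncontrolled trial no comparison arm separates them.

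What is at stake is attribution. The means and confidence-interval plots are the efficacy result of this trial, and SAP 3.2 says the results will form part of a potential marketing application. A reader who takes the objectives at face value would read the visit means as what long-term molgramostim achieves. They are what molgramostim achieves with rescue lavage available.

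**Working it through.** **Step 1. Look for any rule on post-lavage values.** The pooling follows from the absence of a rule, so every place that could hold one was checked.

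| Place in the SAP | Content on lavage and efficacy values |
|---|---|
| 4 Analysis sets; 5.1 Statistical considerations | none |
| 7.2.1, 7.2.6 | exclude oxygen-assisted samples; lavage not mentioned |
| 7.2.2, 7.2.3, 7.2.5 | no condition |
| 7.2.4 | lavage counts, rates, location, saline volume and a listing; no efficacy values |
| 7.2.8 | requirement for treatment by visit, including lavage; no efficacy values |
| 7.4, 7.6, 9 | no imputation, no subgroups, no relevant deviation |
| Lists of tables and figures | nothing split by prior lavage |

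**Step 2. Which endpoints does the documented lavage effect reach?** The protocol names oxygenation and symptoms. (A-a)DO₂ measures oxygenation. DSS is built from symptoms and PaO₂ (Protocol 10.7.5). SGRQ has a symptoms component. For 6MWD, DLCO, FEV₁ and FVC an effect is plausible but not stated.

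**Step 3. Do the lavage and efficacy tables describe the same subjects?** Tables 14.2.4.1–14.2.4.4 use the safety set; the efficacy tables and Table 14.2.8.2 use the full analysis set. The sets differ by subjects never exposed in this trial. SAP 3.2 reports 60 enrolled, of whom 55 were on treatment and 5 were not at termination. Read literally, the difference is at most 5, and fewer if any of those were treated earlier.

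**Step 4. Size.** The plan gives no figure to reproduce: there is no sample size calculation, no lavage frequency and no lavage gain. As an illustration:

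shift in visit mean = (share of summarised subjects with a prior lavage) × (gain still present at the visit)

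Assumed ranges are a share of 5–30% (0.05 × 60 = 3 to 0.30 × 60 = 18 subjects) and a retained gain of 5–20 mmHg.

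- Low: 0.05 × 5 = 0.25 mmHg
- Middle: 0.20 × 10 = 2.0 mmHg
- High: 0.30 × 20 = 6.0 mmHg

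**Step 5. What the shift is measured against.** Let a subject worsen by w from baseline and then gain g from lavage. The observed change is w − g; without rescue it would be w. The gap is g. With w = g = 10 mmHg the observed change is 10 − 10 = 0, against +10 unrescued. The Step 4 figures are therefore distances from the unrescued level, not improvements from baseline.

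**The case against.** The strongest reply is that all-observed summaries are a legitimate treatment-policy description: molgramostim with rescue as needed, and rescue reported as its own endpoint. The trial is descriptive, it stopped early, and SAP 3.2 says the intermittent regimen will likely not appear under posology. Restricting to lavage-free values would favour the drug, because the subjects left are those who did not need rescue. All of this stands, and it is why the all-observed tables should stay. It does not explain why the SAP never says that this is what the tables describe.

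Several stronger readings are tempting and are not supported:

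- *The outputs conceal rescue.* They do not. Lavage by visit and treatment column, Table 14.2.8.2 and the dated listing show how much occurred. Only the link to efficacy values is missing, and a reader would have to merge listings to make it.
- *Lavage-restored lung function and walking distance are reported as drug effect.* The documents state a lavage effect on oxygenation and symptoms only.
- *Up to half of a known drug effect could be spurious.* Dividing 6 by the 12.3 mmHg reduction cited in Protocol 4.1 sets a gap from an unrescued level against a change from baseline in a trial of another product. The two are not comparable.
- *Maintenance of effect is overstated.* In these documents that phrase concerns the period after molgramostim is stopped.
- *The oxygen exclusion implies a lavage exclusion.* Oxygen alters the measurement: FiO₂ enters the (A-a)DO₂ formula, and DSS is defined on room air. Lavage alters the patient, and a room-air value after it remains valid.

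**Conclusion.** The point holds as one of labelling and attribution; it is a cheap improvement, not an error that invalidates an analysis. The visit summaries for (A-a)DO₂, DSS and SGRQ describe molgramostim plus rescue lavage, and the SAP neither says so nor lets a table reader separate the two. For 6MWD and lung function the same is possible but undocumented.

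The size is unknown. The 0.25–6 mmHg range for (A-a)DO₂ rests entirely on the assumed share and retained gain. If few subjects were lavaged, or the gain had faded by the next visit, the shift is small; the added tables would show the share directly.

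**What to change.** 1. Keep the all-observed tables and state, in SAP 7.2 and in the table titles or footnotes, that they include values after rescue WLL.
2. For (A-a)DO₂, 6MWD, SGRQ, DLCO, FEV₁, FVC and DSS, add by-visit and change-from-baseline summaries on the full analysis set, split by WLL since Visit 1 (yes/no, as of that visit). Show n in each group and, for lavaged subjects, the last value before the first WLL. For DSS, use category counts and improved/unchanged/worsened.
3. Flag post-WLL visits in Listings 16.2.6.1–16.2.6.3, 16.2.6.5 and 16.2.6.6.
4. List, rather than tabulate, the assessments around each WLL where they were recorded under Protocol 10.7.7. They exist only where a site performed them, so a table could be largely empty.
5. Amend SAP 7.6 to allow this one descriptive split.

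The cost is SAP wording and programming, since lavage dates are already collected. The drawback is small groups at late visits: with 3 to 18 lavaged subjects spread evenly over three treatment columns, there would be 3/3 = 1 to 18/3 = 6 per column, so the total column will be the readable one. The no-WLL group is also selected for better outcome. The split must be read beside the all-observed tables and the WLL counts, and not as an estimate of drug effect.

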If possible, the 6MWT should be conducted using room air. If a subject is on long-term oxygen therapy, oxygen should be given at their standard flow rate and held constant throughout the test. The tests conducted should be performed using the same oxygen conditions that were used in IMPALA, if possible.

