11. STATISTICS

No formal sample size calculation was done as this is an open-label extension trial. Up to 90 subjects will be included.

Data will be summarised using summary statistics. Continuous data will be presented with the number of observations, mean value, standard deviation, minimum, quartile 1, median, quartile 3 and maximum value. Categorical data will be presented as counts and percentages. The data will be presented by visit in tables and graphs. Individual subject data will be listed. Further details of all analyses will be given in the statistical analysis plan.

No “analysis sets” (intention to treat, per protocol, etc.) are defined. All subjects will be included in the analyses/data presentations (equivalent to a Full Analysis Set).

Only recorded data will be analysed/presented and any subjects who have missing data will only have observed data reported, with no imputation for missing data.

Interim cuts of data may be done on a yearly basis and as needed for regulatory purposes (e.g. 120-day safety update).

Data listings will show all recorded data.

Data from the trial is planned to be combined with relevant data from the IMPALA trial; these combined analyses will be reported separately.

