APPENDIX 4.2 TRIAL SPECIFIC GUIDELINE FOR THE 6MWT 6 MWT AND CR10 (BORG'S) DYSPNOEA SCALE

6MWT

The 6MWT should be conducted according to ATS/ERS technical standard (Field Walking Tests in Chronic Respiratory Disease – Eur Respir J 2014; 44:1428-1446).

The 6MWT should be performed on a flat, straight course with a hard surface with little pedestrian traffic

The walking course should be 30 m or more in length.

The end of the course should be marked such that they are easily visible to patients. The same course should be used at each visit.

The patient should sit at rest in a chair, located near the starting position, for at least 10 minutes before the test starts

The test should be completed with the subject breathing room air, if possible. If a patient is on chronic oxygen therapy and not able to complete the 6MWT on room air, an oxygen titration procedure will be conducted at screening. The procedure described in Appendix 4 should be followed. The same flow of oxygen should then be used at the subject's subsequent tests in the trial, unless a higher flow is required due to the subject's medical condition.

Patients should be encouraged every 60 seconds using standard phrases. Other words of encouragement and other nonverbal prompts should not be used.

If the patient stops walking during the test, the timer must not be stopped. The patient should be allowed to rest while sitting or standing, as they prefer. During the stop, standard encouragement should be given every 30 seconds. The time the patient stopped during the test, should be noted in the eCRF.

If SpO₂ is < 80% then the test should be stopped

Two 6MWTs should be performed (due to the learning effect on the test), and the result from the test with the longest distance walked should be recorded. If the subject is not able to complete more than one test due to exhaustion or adverse events, this should be noted on the worksheet. There must be at least 30 minutes between the two tests.

The total distance walked should be recorded

SpO₂ should be measured using a pulse oximeter continuously during the test. The start value and the lowest value during 6MWT should be recorded

Start heart rate and end heart rate should also be recorded

Use the study-specific worksheet for documenting values, which is provided by sponsor to the sites.

The results from the 6MWT with the longest distance walked and the related SpO₂ and CR10 (Borg) scale results should be entered in the eCRF.

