Standard encouragement during a 6-minute walk test

1 min: You are doing well. You have 5 minutes to go.

2 min: Keep up the good work. You have 4 minutes to go.

3 min: You are doing well. You are halfway.

4 min: Keep up the good work. You have only 2 minutes left.

5 min: You are doing well. You have only 1 minute to go.

6 min: Please stop where you are.

If the patient stops during the test, every 30 s once SpO₂ is $\geq 85\%$ the following standard phrase should be use:

“Please resume walking whenever you feel able.”

CR10 Scale/Borg’s dyspnoea scale

The CR10 (Borg’s) scale for dyspnoea provided by Savara should be rated before and after the 6MWT. Let the patient read the instruction before rating their dyspnoea on the CR10 scale. Standard instructions for the CR10 (Borg scale) will be provided in local language.

If possible, the test should be conducted using the same oxygen flow level as was used in IMPALA. If a subject has started chronic oxygen therapy after being enrolled in IMPALA, an oxygen titration procedure should be conducted as described below.

This procedure only applies for patients on chronic oxygen supplementation at screening:

The patient will perform an O₂ titration procedure at Screening to determine the amount of supplemental oxygen that the patient needs to complete the 6MWT without developing O₂ desaturation. This oxygen flow rate will represent the patient’s baseline O₂ flow rate for all subsequent 6MWT procedures for this study.

Equipment and supplies:

The equipment and supplies needed for the Oxygen Titration Procedure are the same as those needed for the 6MWT. Verify that your oxygen flow meter is accurate (to within 0.5 liters per minute).

Patient safety:

The safety precautions for the Oxygen titration procedure at the screening visit are same as required for the 6MWT.

Procedure:

Step 1: Resting O₂ Titration

Attach the pulse oximeter. Set it to alarm when SpO₂ falls below 83%.

Instruct the patient to sit still and not chat.

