Savara received advice on the MOL-PAP-002 trial results from EMA and FDA. The data demonstrated more favorable evidence of efficacy on the continuous dosing regimen. Following the advice Savara has subsequently decided to conduct an additional Phase III confirmatory trial to support future registration of the continuous dosing regimen. The SAV006-03 trial investigates an intermittent dosing regimen but considering the MOL-PAP-002 clinical trial results and the received health authority advice there will not be adequate efficacy and safety data on the intermittent dosing regimen to support a marketing authorization application for this regimen. Consequently, Savara has decided to discontinue the SAV006-03 trial and support the continued clinical investigation of the continuous dosing regimen in a new trial.

60 subjects have been enrolled in the SAV006-03 trial and enrolled subjects will be able to continue treatment until end of 2020. Of these, 55 subjects are on active treatment and 5 subjects do not receive treatment at the time of trial termination. The 5 subjects have been allowed to remain in the trial to observe development of their disease without receiving treatment.

The data from the SAV006-03 trial will be included in the ongoing safety evaluation of molgramostim nebulizer solution. The results of the SAV006-03 trial will also be included as part of a potential future marketing authorization application for use of molgramostim nebulizer solution as a potential treatment for autoimmune pulmonary alveolar proteinosis, although the intermittent dosing regimen will likely not be included as a treatment regimen under posology.

All generated data will be cleaned and assessed according to plan and will contribute to the risk-benefit profile for molgramostim. The trial will be reported according to ICH GCP requirements.

Table 1 Activities flow chart

Table 1: Visit	Visit 1	Visit 2	Visit 3	Visit 4	Visit 5	Visit 6	Visit 7	FU TC	Unscheduled
	Baseline ^a	Month 6	Month 12	Month 18	Month 24	Month 30	Month 36	2 wks after trial completion	
Time	0	Week 26	Week 52	Week 78	Week 104	Week 130	Week 156		
Visit Window	N/A	± 4wks	± 4 wks	± 4 wks	± 4 wks	± 4 wks	± 4 wks	+ 1 wk	
Informed consent	X								
Eligibility criteria	X								
Demographics	X								
Concomitant medication	X	X	X	X	X	X	X		X
WLL information ^b	X	X	X	X	X	X	X		X
Pregnancy test and contraceptive check ^c	X	X	X	X	X	X	X		(X) ^d
Physical Exam	(X)		X		X		X		(X) ^d
Vital signs	(X)	X	X	X	X	X	X		(X) ^d

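### The 6-minute walk summaries take no account of oxygen used during the walk, so change from baseline mixes oxygen effect with exercise capacity whenever that oxygen changes after the baseline test

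*SAP*

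**What the plan says.** **Analysis.** SAP 7.2.2 states: "Distance in meter, Borg score endpoints, and SpO₂ and the desaturation (first SpO₂-worst SpO₂) will be summarized by treatment and visit". Two walks are done at each visit, and "the results from the test with the longest distance walked will be used in the reporting of the trial". Tables 14.2.2.1 to 14.2.2.12, which include the change-from-baseline tables, and Figures 14.2.2.1 to 14.2.2.6 use the full analysis set. None is split or restricted by oxygen. Oxygen use and flow during each walk are shown only in the walk-test listing.

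Two other endpoints are handled differently. For (A-a)DO₂, SAP 7.2.1 states: "Subjects on supplementary oxygen during blood gas sample are excluded from the relevant visits in the summary". SAP 7.2.6 likewise drops on-oxygen visits from both DSS tables.

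**Conduct.** Protocol 10.7.2 prefers room air and has subjects on long-term oxygen walk at their standard flow. It adds: "The tests conducted should be performed using the same oxygen conditions that were used in IMPALA, if possible". Table 1 note g makes the same qualified request. Appendix 4.2 keeps the flow the same at later tests "unless a higher flow is required due to the subject's medical condition". It also says: "If a subject has started chronic oxygen therapy after being enrolled in IMPALA, an oxygen titration procedure should be conducted as described below".

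**Baseline.** SAP 5.1 takes the Visit 1 value before the first dose in this trial, or the nearest IMPALA value if that is missing. Table 1 note a lets the final IMPALA visit serve as Visit 1.

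**The concern.** Walking distance is the endpoint for the exercise-capacity objective. The trial has no control group, so change within subjects carries most of the information and no concurrent arm would expose an artefact. Supplemental oxygen is likely to change as the disease changes, and it also acts on the measurements. A subject who worsens and is given oxygen may show a steady distance and a steady worst SpO₂. A subject who improves and comes off oxygen may show no gain. A reader of the mean tables and plots could not tell either case from a stable subject.

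No error rate is at stake, because the summaries are descriptive. What is at stake is the reading of a secondary endpoint whose results, according to SAP 3.2, would form part of a potential marketing application.

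**Working it through.** **No planned figure to reproduce.** Protocol section 11 states: "No formal sample size calculation was done as this is an open-label extension trial". The documents give no expected walk distance, SpO₂ value or standard deviation. The check therefore compares passages and adds an illustration on assumed values.

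**Step 1: can walk oxygen differ between visits?** Yes. Constancy with IMPALA is asked for only where possible, and Appendix 4.2 permits a higher flow. SAP 7.2.7 plans tables for oxygen in progress at baseline and at the end of the trial, and for oxygen both started and stopped in between. The plan therefore foresees changes in use.

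**Step 2: which changes matter?** Only those after the baseline walk. A subject on the same flow throughout has no within-subject distortion. A subject who began oxygen during IMPALA and already walked on it at Visit 1 has an on-oxygen baseline and is unaffected unless the flow later changes.

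**Step 3: direction, by variable.**
- *Worst SpO₂.* The Appendix 4.2 titration selects the lowest flow at which the walk is completed without SpO₂ falling below 83%. For a titrated subject the variable is partly set by the procedure.
- *Distance.* Appendix 4.2 stops a walk if SpO₂ is below 80%. A subject who would be stopped on room air may finish on oxygen, so a gain is plausible.
- *Desaturation.* This is start minus worst, and oxygen can raise both. Take a hypothetical subject:

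| Walk | Start / worst SpO₂ | Desaturation | Change in worst | Change in desaturation |
|---|---|---|---|---|
| Baseline, room air | 92 / 84 | 8 | – | – |
| Later, if on room air | 89 / 78 | 11 | −6 | +3 |
| Later, on oxygen (A) | 95 / 86 | 9 | +2 | +1 |
| Later, on oxygen (B) | 97 / 86 | 11 | +2 | +3 |

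The fall in worst SpO₂ is hidden in both A and B. The rise in desaturation is partly hidden in A and fully visible in B.

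**Step 4: illustration of size.** Shift in a visit mean = (share on more oxygen × effect) − (share on less oxygen × effect). The SAP gives the total: "60 subjects have been enrolled in the SAV006-03 trial". The shares and effects below are assumptions, with nobody on less oxygen.

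| Share on more oxygen | Distance, effect 20 to 80 m | Worst SpO₂, effect 3 to 8 points |
|---|---|---|
| 3/60 = 5% | 1.0 to 4.0 m | 0.15 to 0.40 |
| 6/60 = 10% | 2.0 to 8.0 m | 0.30 to 0.80 |
| 12/60 = 20% | 4.0 to 16.0 m | 0.60 to 1.60 |

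The sign can reverse. With an effect of 50 m, 5% on more oxygen and 10% on less, the shift is 0.05 × 50 − 0.10 × 50 = 2.5 − 5.0 = −2.5 m. With equal shares it is zero. Results are shown in three columns. If these were equal (60/3 = 20, an assumption), one subject would be 1/20 = 5% of a column.

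**The case against.** **The comparison with (A-a)DO₂ and DSS is imperfect.** A reader might infer that the SAP contradicts itself by excluding on-oxygen visits there but not here. That goes too far. Protocol 10.7.5 bases DSS on PaO₂ breathing room air, so the exclusion brings DSS back to its definition, and (A-a)DO₂ is calculated from the inspired oxygen fraction. The walk test has no room-air definition, and the protocol expects some subjects to walk on oxygen. The comparison shows that oxygen was considered for other endpoints, not that the same rule must apply. This part of the objection stands.

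**Constant oxygen is the default.** This also stands, and it limits the number of subjects affected. It does not correct the tables for those whose oxygen does change.

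**Oxygen need is tabulated.** Tables 14.2.7.1 to 14.2.7.5 cover it. Subjects newly on oxygen at the end are 14.2.7.3 minus 14.2.7.4, and those who came off are 14.2.7.2 minus 14.2.7.4. Worsening that leads to new long-term oxygen is therefore not invisible. But these tables are drawn from concomitant medication and are not by visit. They do not show a flow that was only raised or lowered, and they are not linked to the walk.

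**The listing shows flow.** It lets a reader find affected subjects one at a time, but it adjusts no summary or plot.

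**Excluding visits brings its own bias.** This stands. Dropping visits with changed oxygen removes subjects who are worsening or improving. It argues against room-air-only tables for every variable and for showing counts beside any restricted table.

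**Conclusion.** The gap is real. Under SAP 7.2.2, a change in walk oxygen after the baseline test enters the change-from-baseline results as if it were a change in exercise capacity or exertional oxygenation. The conclusion is firm for worst SpO₂, plausible for distance, and uncertain for desaturation.

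A reader might infer that the tables are biased in favour of the drug. The documents do not support this. Starting or raising oxygen flatters the result, while lowering or stopping it does the reverse, and the balance between the two is not given. The shifts of 1 to 16 m and 0.15 to 1.6 points rest wholly on assumed shares and effects and on nobody reducing oxygen. They show scale and are not estimates.

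The point concerns the interpretation of secondary endpoints in a descriptive trial whose primary objective is safety. It merits a modest addition to the SAP and does not call the trial's main conclusions into question.

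**What to change.** Keep the all-subject tables in SAP 7.2.2 and add:

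1. For each visit and treatment column, the number walking on oxygen and the number whose flow was higher than, equal to or lower than at the baseline walk, counting room air as zero flow.
2. A supportive change-from-baseline summary of 6MWD and worst SpO₂, limited to subject-visits where oxygen use and flow match the baseline walk. Base the match on the walk selected for reporting (the longest). State that this table must be read beside item 1, because the excluded visits are not a random subset.

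The sponsor should also reconcile the passages on walk oxygen. Protocol 10.7.2 refers both to the subject's standard flow and to the IMPALA conditions, and Table 1 note g to the IMPALA flow. Appendix 4.2 refers to a titrated flow fixed for all later walks and also to a higher flow when required. It ties titration to screening, but Table 1 has no screening visit. Which rule should apply is for the sponsor to settle.

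**Cost.** A few extra tables and smaller numbers in the restricted summary. Flow and oxygen use during the walk are already recorded in this trial. Where the baseline walk is taken from IMPALA, its flow must come from that trial's data; the documents do not say how it is stored.
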